6.1 Primary objective

The primary objective for this safety registry study for voretigene neparvovec is to collect all AESIs, as well as any other AEs and SAEs.

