A patient will be considered potentially lost to follow-up if they do not return to the study site for the annual follow-up visits and no information can be obtained via telephone contact or other sources. The site is encouraged to make every effort (phone, email, certified mail) and document those efforts to regain contact to resume data collection. A patient cannot be considered as lost to follow-up until the time point of their scheduled End of Study visit has passed.

Variables

The safety profile of voretigene neparvovec, administered to patients who enroll in this study, should be evaluated based on the examination of general demographic and safety variables, including specific clinical measures.

Pre-treatment and Baseline characteristics

- Demographics (e.g. age, gender, race, ethnicity, and country of residence)
- Medical and surgical history (including prior gene and cell therapy)
- Ocular characteristics (including information on viable cells and ophthalmic exam results)
- Genetic diagnosis related to the inherited retinal dystrophy
- Clinical diagnoses related to the inherited retinal dystrophy
- Concomitant medications and procedures
- PRO and caregiver questionnaires

Voretigene neparvovec administration information

- Surgical center location
- Date of injection(s) (right eye, left eye)
- Lot number and volume administered (right eye, left eye)
- Details of perioperative corticosteroids use
- Surgical details including number and location of retinotomies (right eye, left eye)

Safety Variables

- The following events are designated as AESIs and will be queried through the standardized safety questionnaire ([Section 12.1](#)) and entered into the AE CRF:
 - Ocular AEs
 - Lack of efficacy and/or decline in efficacy over time*
 - Third-party transmission
 - Host immune response
 - Development or exacerbation of oncologic, hematologic, neurologic, or auto-immune diseases
- ***Note:** Signs and symptoms resulting from “lack of efficacy” or “decline of efficacy over time” or “failure of expected pharmacological action” should be provided in the AE or SAE description.
- Follow-up information on reported chorioretinal atrophy
- Any other AEs and SAEs
- Information on pregnancy occurrence, outcomes, and lactation (from patients and female partners of patient)
- Ophthalmic examination results for VA, VF, FST, and OCT:

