For patients enrolled under protocol version 02			
For all protocol versions			
BIC (Section 12.5)	X ^b		X
Safety Variables			
Ophthalmic examination: visual acuity (VA), visual field (VF), full-field light sensitivity threshold testing (FST), and optical coherence tomography (OCT)	X ^c		X
All AEs of special interest (AESIs): ocular AEs, lack of efficacy and/or decline of efficacy over time, third-party transmission, host immune response, and development or exacerbation of oncologic, hematologic, neurologic, or auto-immune diseases (NOTE: Collection must be assessed at each visit in accordance with the standardized safety questionnaire)		X	X

Assessments	Pre-treatment/ baseline data collection point	Post- treatment data collection point	Follow-Up data collection point (Years 1-5)
Any other AEs or SAEs		X	X
Pregnancy occurrence and outcomes (from both patient and female partners of patient), including whether any child was breastfed		X	X
End of study visit			X

a - Concomitant medications taken and procedures performed within 30 days prior to voretigene neparovec treatment.

b - Baseline questionnaire to be completed prior to voretigene neparovec treatment.

c - Most recent ophthalmic examinations performed within 3 months prior to voretigene neparovec treatment.

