12.1 Safety Questionnaire

Patient ID: _____

Date of Visit _____

Since the patient's last visit, has s/he experienced:

Ocular Event	No	Yes*, Right Eye (OD)	Yes*, Left Eye (OS)	Yes*, Both Eyes (OU)	Start Date	Ongoing/ End Date
Increased Intraocular Pressure						
Retinal Tear						
Macular Disorders						
• Macular Hole						
• Foveal Dehiscence						
• Maculopathy (e.g., epiretinal membrane, macular pucker)						
• Foveal thinning						
• Loss of foveal function						
Chorioretinal atrophy (e.g. injection site atrophy/treatment emergent progressive atrophy)						
Cataract						
Intraocular Inflammation and/or Infection Related to the Procedure						
Retinal Detachment						
Host Immune Response (Ocular)						
Lack of Efficacy						
Decline in Efficacy over Time						
Other ocular event, specify						

Event	No	Yes*	Start Date	Ongoing/ End Date
New or exacerbated neoplastic event, specify				
Third Party Transmission				
Host Immune Response (Non-ocular)				
New or exacerbated hematologic event, specify				
New or exacerbated neurologic event, specify				

***NOTE: If YES to any of the above, the event(s) MUST be reported as an Adverse Event or Serious Adverse Event and documented in eCRFs**

***NOTE: If yes to any of the above, please provide a narrative of the event(s), including relevant information (e.g., presenting signs or symptoms, relevant associated medical or ocular conditions, concomitant medications, tests performed to assess the event and results, treatment given for the event, etc).**

Event:
 
Narrative:

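### The safety questionnaire has no auto-immune item, although the protocol designates auto-immune disease as an AESI to be queried through it

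*Protocol*

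**What the plan says.** The primary objective (Protocol Section 6.1) "is to collect all AESIs, as well as any other AEs and SAEs". Section 7.2, under Safety Variables, introduces the AESI list with "The following events are designated as AESIs and will be queried through the standardized safety questionnaire". The last category on that list is "Development or exacerbation of oncologic, hematologic, neurologic, or auto-immune diseases". Section 9.1 lists the same category.

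Table 7-1 (Section 7.3) names it again as "development or exacerbation of oncologic, hematologic, neurologic, or auto-immune diseases" and adds the note "Collection must be assessed at each visit in accordance with the standardized safety questionnaire".

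The form in Section 12.1 has an ocular table and a non-ocular table. The non-ocular table has five rows:
- "New or exacerbated neoplastic event, specify"
- third-party transmission
- non-ocular host immune response
- "New or exacerbated hematologic event, specify"
- "New or exacerbated neurologic event, specify"

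The footnotes follow directly. They require any positive answer to be reported as an AE or SAE and described in a narrative. The ocular table closes with an open row for other ocular events; the non-ocular table has no counterpart.

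**The concern.** The questionnaire is the protocol's device for making AESI ascertainment uniform across sites that otherwise follow routine care. Section 7.8 concedes that, without standardized assessment procedures, the study cannot account for information bias, so the form carries much of what standardization there is.

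A completed form documents that a patient was asked about neurologic, hematologic and neoplastic events, and what the answer was. It cannot document this for auto-immune disease, and it gives the site no line that triggers the AE report and narrative. A zero for auto-immune disease in a progress report or the final report would not carry the same evidence as a zero for the prompted groups. Yet the AESI list puts all four in one category, collected under the primary objective.

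**Working it through.** No published figure is involved, so the check is a line-by-line comparison of the AESI list (Sections 7.2 and 9.1, Table 7-1) with the rows of the form (Section 12.1).

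| Designated AESI | Row on the form |
|---|---|
| Ocular AEs | Yes: named ocular rows plus an open row |
| Lack or decline of efficacy | Yes: two rows |
| Third-party transmission | Yes |
| Host immune response | Yes: one ocular row, one non-ocular row |
| Oncologic disease | Yes, as neoplastic |
| Hematologic disease | Yes |
| Neurologic disease | Yes |
| Auto-immune disease | **None** |

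Within the last AESI category, 3 of 4 disease groups have a row and 1 of 4 has none. Every other AESI has at least one row.

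Could another row stand in for the missing one?
- *Host immune response.* All three places that list the AESIs name it separately from auto-immune disease. By the protocol's own classification it is a different event.
- *An open row.* Only the ocular table has one.

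What other routes does the protocol provide?
- Sections 2, 7.2 and 9.1 instruct sites to question patients specifically on each AESI at each visit. Auto-immune disease is on the list, so the duty to ask covers it.
- Sections 2 and 7.2 add a question about any other AEs or SAEs. Section 9.1 adds non-directive questioning.
- Section 9.1 uses the form together with clinical observations and ophthalmic results, and requires all AEs to be recorded, including those between dosing and enrollment.
- Section 7.2 allows data from other treating physicians and provides a patient card.

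The event can therefore reach the database. The missing element is the uniform, recorded prompt that Section 7.2 and Table 7-1 say exists.

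On scale, Section 7.4 expects at least 40 patients. At exactly 40, one patient with a missed event moves the reported incidence by 1/40 = 2.5 percentage points. This shows how coarse the estimate is; it does not say how likely a miss is. The protocol gives no capture rate, prompted or unprompted, so the extent of any undercount cannot be calculated.

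**The case against.** The strongest reply is that nothing is lost, because sites must ask about every AESI whether or not the form has a line for it, and all AEs are recorded by whatever route they arrive. Much of this stands. A reader might infer from the missing row that auto-immune disease is never solicited, or comes to light only through open questions. The documents do not support either reading, because the instruction to question on each AESI includes it. A reader might also want to put a percentage on the undercount. Any such figure would merely restate an assumed capture rate.

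It can also be said that auto-immune disease is not among the important risks named in Section 5, that it is one of four groups within one AESI category, and that the output is purely descriptive, with no test or decision rule resting on the count. These points limit the consequence.

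They do not remove the contradiction. Section 7.2 says the AESIs are queried through this form, Table 7-1 requires collection in accordance with it, and the form does not contain the item. A general instruction to ask is not the same as a prompt whose answer is recorded each time.

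**Conclusion.** The point holds as an inconsistency between the AESI list and the instrument meant to collect it. One of the four disease groups in the last AESI category lacks the standardized yes/no item that the other three have, on every form completed under this version. Auto-immune events remain reportable and must be recorded. Their ascertainment may be less complete and less uniform than for the other three groups, and standardized prompting cannot be demonstrated from the form. The size of the effect is unknown.

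This rests on the non-ocular table being complete as read. A row lost when the PDF was converted is possible but unlikely, since the table runs straight into its footnotes. It also assumes that the eCRF mirrors the annex; if the eCRF already has an auto-immune item, only the annex needs correcting.

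**What to change.** Add a row to the non-ocular table in Section 12.1, and to the eCRF, worded like its neighbours: *New or exacerbated auto-immune event, specify*. In the progress reports and the final report, state the date from which the form prompted for auto-immune events, so that counts before and after it are read accordingly.

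A single look-back question at the next visit of patients already enrolled is optional. It would extend the prompt to elapsed follow-up, but it relies on longer recall and mixes two ways of ascertaining events, and AEs since dosing must already be recorded in any case. If it is used, the reports should say so.

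The cost is one row on the form and eCRF and one sentence in each report, plus one question per enrolled patient if the look-back is used. Version 02 already changed this form to add chorioretinal atrophy, so there is a precedent for an amendment of this kind. Data collection is planned to run to December 2029, and an early change covers more of the follow-up.

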12.2 Modified VFQ-25 Questionnaire

This questionnaire should be completed for participants who were enrolled under the original protocol version 01.

Adult participants:

- Participants should complete the questionnaire, but due to limited vision, may need assistance.

Minor participants:

1. Parent/guardian should complete one copy of the questionnaire and provide their perspective of the participant's vision.
2. The participant should complete a second copy of the questionnaire to provide his/her perspective in collaboration with the parent/guardian as needed.
 - If the participant is very young, it is expected that the parent/guardian will assist the child as needed to answer the questions and to complete the questionnaire. It is desirable that the parent/guardian will contribute less as the child ages. By the time the child becomes a young teenager, it is assumed that the teenager themselves will provide the questionnaire responses. However, the parent/caregiver may assist as needed.

This questionnaire should be completed by the same parent/guardian throughout the duration of the study, if possible.

7. Can you read normal print books or see details in pictures without magnifiers or computer/television screens?
- Never Sometimes Always Not Answered
- 0 1 2 3 4 5 6 7 8 9 10
8. Can you see a movie in a theater, or a planetarium show?
- Never Sometimes Always Not Answered
- 0 1 2 3 4 5 6 7 8 9 10
9. Using your vision (only), can you find your plate, fork and spoon in a restaurant that is dimly lit?
- Never Sometimes Always Not Answered
- 0 1 2 3 4 5 6 7 8 9 10
10. Can you read labels on cans/food products/medicine bottles?
- Never Sometimes Always Not Answered
- 0 1 2 3 4 5 6 7 8 9 10
11. Can you read street signs or signage in buildings (such as STOP and EXIT signs)?
- Never Sometimes Always Not Answered
- 0 1 2 3 4 5 6 7 8 9 10

For the following questions, an answer of “0” means “Always”:

12. Using your vision (only), do you have difficulty judging whether someone is male or female?
- Always Sometimes Never Not Answered
- 0 1 2 3 4 5 6 7 8 9 10
13. Using your vision (only), do you have trouble determining the expression (happy, sad, neutral) on unfamiliar faces?
- Always Sometimes Never Not Answered
- 0 1 2 3 4 5 6 7 8 9 10
14. Do you have trouble identifying simple shapes (circle, rectangle, square)?
- Always Sometimes Never Not Answered
- 0 1 2 3 4 5 6 7 8 9 10

15. Do you have difficulty seeing which direction hands on a clock (non-digital) are facing?

Always	Sometimes	Never	Not Answered
0	1 2 3 4 5 6 7 8 9	10	

16. Do you put things down in specific places so that you can find them by feel/touch?

Always	Sometimes	Never	Not Answered
0	1 2 3 4 5 6 7 8 9	10	

17. When using your vision alone and in good light, do you make mistakes when dressing (e.g. mismatched socks, wrong outfit, confusing left vs. right shoe)?

Always	Sometimes	Never	Not Answered
0	1 2 3 4 5 6 7 8 9	10	

18. When using your vision alone, do you make mistakes when using the bathroom or bathing (e.g. unable to locate bottles, bathroom fixtures)?

Always	Sometimes	Never	Not Answered
0	1 2 3 4 5 6 7 8 9	10	

19. In your home or school environment, if someone accidentally leaves a cabinet door, a gate, a locker door, or some other moveable object in a new position, are you likely to bump into it?

Always	Sometimes	Never	Not Answered
0	1 2 3 4 5 6 7 8 9	10	

20. Do you need assistance such as a guide or a cane to walk confidently in new places?

[figure not shown]
Always	Sometimes	Never	Not Answered
0	1 2 3 4 5 6 7 8 9	10	

[figure not shown]
21. In unfamiliar surroundings, how often do you run into things by mistake (e.g. stub your toe, hit your shoulder, trip)?

[figure not shown]
Always	Sometimes	Never	Not Answered
0	1 2 3 4 5 6 7 8 9	10	

[figure not shown]
22. In familiar surroundings, how often do you get lost or disoriented, even briefly?

[figure not shown]
Always	Sometimes	Never	Not Answered
0	1 2 3 4 5 6 7 8 9	10	

[figure not shown]

[figure not shown]

[figure not shown]

[figure not shown]

[figure not shown]

[figure not shown]

[figure not shown]

[figure not shown]

[figure not shown]

[figure not shown]

[figure not shown]

[figure not shown]

[figure not shown]

[figure not shown]

[figure not shown]

[figure not shown]

12.5 Burden Index of Caregivers

This questionnaire should be completed by the parent/guardian/caregiver.

- Whenever possible, the same person should complete the questionnaire throughout the duration of the study.

Patient ID: _____

Date of visit: _____

Using the following legend, select how you felt during the last week;

0 – Never / 1 – Almost never / 2 – Sometimes / 3 – Often / 4 – Always

1. I cannot freely leave the house because of care-giving	
2. I do not have enough time for myself because of care-giving	
3. I want to delegate the care to someone else	
4. I am completely distressed by care-giving	
5. I am experiencing hardship because care-giving does not give me a sense of satisfaction	
6. Care-giving is hard because I cannot find the meaning of providing care	
7. My body aches when providing care to my family member	
8. I have ruined my health in the course of providing care	
9. It is a burden that public aid service personnel enter our house	
10. I have a hard time because patients resent receiving public aid care services	
11. How burdensome do you think providing care is to you?	

12.6 ENCePP checklist for study protocol

EUROPEAN MEDICINES AGENCY
SCIENCE MEDICINES HEALTH

European Network of Centres for Pharmacoepidemiology and Pharmacovigilance (ENCePP)

Doc.Ref. EMA/540136/2009

ENCePP Checklist for Study Protocols (Revision 4)

Adopted by the ENCePP Steering Group on 15/10/2018

The European Network of Centres for Pharmacoepidemiology and Pharmacovigilance (ENCePP) welcomes innovative designs and new methods of research. This Checklist has been developed by ENCePP to stimulate consideration of important principles when designing and writing a pharmacoepidemiological or pharmacovigilance study protocol. The Checklist is intended to promote the quality of such studies, not their uniformity. The user is also referred to the ENCePP Guide on Methodological Standards in Pharmacoepidemiology, which reviews and gives direct electronic access to guidance for research in pharmacoepidemiology and pharmacovigilance.

For each question of the Checklist, the investigator should indicate whether or not it has been addressed in the study protocol. If the answer is “Yes”, the section number of the protocol where this issue has been discussed should be specified. It is possible that some questions do not apply to a particular study (for example, in the case of an innovative study design). In this case, the answer ‘N/A’ (Not Applicable) can be checked and the “Comments” field included for each section should be used to explain why. The “Comments” field can also be used to elaborate on a “No” answer.

This Checklist should be included as an Annex by marketing authorisation holders when submitting the protocol of a non-interventional post-authorisation safety study (PASS) to a regulatory authority (see the Guidance on the format and content of the protocol of non-interventional post-authorisation safety studies). The Checklist is a supporting document and does not replace the format of the protocol for PASS presented in the Guidance and Module VIII of the Good pharmacovigilance practices (GVP).

Study title:

A Post-Authorization, Multicenter, Multinational, Longitudinal, Observational Safety Registry Study for Patients Treated with Voretigene Neparvovec

EU PAS Register® number: EUPAS31153

Study reference number: CLTW888A12401

Section 1: Milestones	Yes	No	N/A	Section Number
1.1 Does the protocol specify timelines for				
1.1.1 Start of data collection ¹				4
1.1.2 End of data collection ²				4
1.1.3 Progress report(s)				4
1.1.4 Interim report(s)				
1.1.5 Registration in the EU PAS Register®				4
1.1.6 Final report of study results.				4
^{1.} Date from which information on the first study is first recorded in the study dataset or, in the case of secondary use of data, the date from which data extraction starts. ^{2.} Date from which the analytical dataset is completely available.				

Comments:

Progress reports will be provided annually – no other interim reports are planned.

Section 2: Research question	Yes	No	N/A	Section Number
2.1 Does the formulation of the research question and objectives clearly explain:				
2.1.1 Why the study is conducted? (e.g. to address an important public health concern, a risk identified in the risk management plan, an emerging safety issue)				5 and 6
2.1.2 The objective(s) of the study?				6
2.1.3 The target population? (i.e. population or subgroup to whom the study results are intended to be generalised)				7.2
2.1.4 Which hypothesis(-es) is (are) to be tested?				
2.1.5 If applicable, that there is no a priori hypothesis?				

Comments:

Safety variables will be summarized by descriptive statistics. No inferential analysis will be done and no hypothesis will be tested. There is no *a priori* hypothesis to be tested.

Section 3: Study design	Yes	No	N/A	Section Number
3.1 Is the study design described? (e.g. cohort, case-control, cross-sectional, other design)				7.1
3.2 Does the protocol specify whether the study is based on primary, secondary or combined data collection?				7.3
3.3 Does the protocol specify measures of occurrence? (e.g., rate, risk, prevalence)				7.6
3.4 Does the protocol specify measure(s) of association? (e.g. risk, odds ratio, excess risk, rate ratio, hazard ratio, risk/rate difference, number needed to harm (NNH))				
3.5 Does the protocol describe the approach for the collection and reporting of adverse events/adverse reactions? (e.g. adverse events that will not be collected in case of primary data collection)				9

Comments:

This study is intended to descriptively document the frequency and severity of events of interest. No measures of association will be presented.

Section 4: Source and study populations	Yes	No	N/A	Section Number
4.1 Is the source population described?				7.2
4.2 Is the planned study population defined in terms of:				
4.2.1 Study time period				7.2
4.2.2 Age and sex				7.2
4.2.3 Country of origin				
4.2.4 Disease/indication				
4.2.5 Duration of follow-up				7.2
4.3 Does the protocol define how the study population will be sampled from the source population? (e.g. event or inclusion/exclusion criteria)				7.2

Comments:

This is a product registry – patients who receive voretigene neparvovec treatment are eligible. Information on the clinical and genetic diagnoses of the condition that led to voretigene neparvovec treatment will be collected.

This registry will be conducted in multiple countries, and patients can be included regardless of country of origin where Luxturna® is marketed.

Section 5: Exposure definition and measurement	Yes	No	N/A	Section Number
5.1 Does the protocol describe how the study exposure is defined and measured? (e.g. operational details for defining and categorising exposure, measurement of dose and duration of drug exposure)				7.2
5.2 Does the protocol address the validity of the exposure measurement? (e.g. precision, accuracy, use of validation sub-study)				7.7.1
5.3 Is exposure categorised according to time windows?				
5.4 Is intensity of exposure addressed? (e.g. dose, duration)				7.2
5.5 Is exposure categorised based on biological mechanism of action and taking into account the pharmacokinetics and pharmacodynamics of the drug?				
5.6 Is (are) (an) appropriate comparator(s) identified?				

Comments:

Voretigene neparvovec is administered by specialist ophthalmologists (retinal surgeons) as a single dose to each eye in a hospital setting. Exposure data will be collected in the medical records. There are no appropriate comparators for this treatment.

Section 6: Outcome definition and measurement	Yes	No	N/A	Section Number
6.1 Does the protocol specify the primary and secondary (if applicable) outcome(s) to be investigated?				6.1, 6.2 & 7.6
6.2 Does the protocol describe how the outcomes are defined and measured?				7.3 and 7.6

Section 6: Outcome definition and measurement	Yes	No	N/A	Section Number
6.3 Does the protocol address the validity of outcome measurement? (e.g. precision, accuracy, sensitivity, specificity, positive predictive value, use of validation sub-study)				
6.4 Does the protocol describe specific outcomes relevant for Health Technology Assessment? (e.g. HRQoL, QALYs, DALYS, health care services utilisation, burden of disease or treatment, compliance, disease management)				7.2 and 7.3

Comments:

This study is intended to descriptively document the frequency and severity of reported events of interest. There are no additional measures to address the validity of the outcome measurements. The mVFQ-25, [REDACTED] response scores will be summarized by descriptive statistics to provide HRQoL data. The Burden Index of Caregivers (BIC) Questionnaire will be administered to obtain data describing the burden of care-giving imposed by the disease.

Section 7: Bias	Yes	No	N/A	Section Number
7.1 Does the protocol address ways to measure confounding? (e.g. confounding by indication)				
7.2 Does the protocol address selection bias? (e.g. healthy user/adherer bias)				
7.3 Does the protocol address information bias? (e.g. misclassification of exposure and outcomes, time-related bias)				

Comments:

As described in Section 7.8, the lack of randomization and a control group in this single arm study is not able to account for selection bias. The observational nature of the study, without using standardized assessment procedures, is also not able to account for potential information bias. Nonetheless, this study design will be able to describe what is observed when voretigene neparvovec is used in the real-world setting, when patients are treated as per the current standard of care.

Section 8: Effect measure modification	Yes	No	N/A	Section Number
8.1 Does the protocol address effect modifiers? (e.g. collection of data on known effect modifiers, subgroup analyses, anticipated direction of effect)				7.6

Comments:

Analysis by age categories is planned.

Section 9: Data sources	Yes	No	N/A	Section Number
9.1 Does the protocol describe the data source(s) used in the study for the ascertainment of:				
9.1.1 Exposure? (e.g. pharmacy dispensing, general practice prescribing, claims data, self-report, face-to-face interview)				7.3
9.1.2 Outcomes? (e.g. clinical records, laboratory markers or values, claims data, self-report, patient interview including scales and questionnaires, vital statistics)				7.3
9.1.3 Covariates and other characteristics?				7.3
9.2 Does the protocol describe the information available from the data source(s) on:				
9.2.1 Exposure? (e.g. date of dispensing, drug quantity, dose, number of days of supply prescription, daily dosage, prescriber)				7.3
9.2.2 Outcomes? (e.g. date of occurrence, multiple event, severity measures related to event)				7.3
9.2.3 Covariates and other characteristics? (e.g. age, sex, clinical and drug use history, co-morbidity, co-medications, lifestyle)				7.3
9.3 Is a coding system described for:				
9.3.1 Exposure? (e.g. WHO Drug Dictionary, Anatomical Therapeutic Chemical (ATC) Classification System)				
9.3.2 Outcomes? (e.g. International Classification of Diseases (ICD), Medical Dictionary for Regulatory Activities (MedDRA))				7.6.2
9.3.3 Covariates and other characteristics?				
9.4 Is a linkage method between data sources described? (e.g. based on a unique identifier or other)				7.7.2

Comments:

This is a product registry for patients who receive voretigene neparvovec treatment. No additional coding of the exposure is required.

This study is intended to descriptively document the frequency and severity of reported events of interest. There is no additional coding for covariate. Each patient would have a unique patient ID which could be used to link CRF information with source documents.

Section 10: Analysis plan	Yes	No	N/A	Section Number
10.1 Are the statistical methods and the reason for their choice described?				7.6
10.2 Is study size and/or statistical precision estimated?				
10.3 Are descriptive analyses included?				7.6
10.4 Are stratified analyses included?				
10.5 Does the plan describe methods for analytic control of confounding?				
10.6 Does the plan describe methods for analytic control of outcome misclassification?				
10.7 Does the plan describe methods for handling missing data?				
10.8 Are relevant sensitivity analyses described?				

Comments:

There is no formal sample size estimation. Every effort will be made to enroll all patients treated with voretigene neparovec, and it is expected that a minimum of 40 adult or pediatric, male or female patient can be enrolled over a five year enrollment period.

No formal statistical evaluations are planned. Output will be limited to data listings and descriptive statistics, where applicable.

Detailed methods for handling missing data will be described in a separate Statistical Analysis Plan document.

Section 11: Data management and quality control	Yes	No	N/A	Section Number
11.1 Does the protocol provide information on data storage? (e.g. software and IT environment, database maintenance and anti-fraud protection, archiving)				7.7
11.2 Are methods of quality assurance described?				7.7
11.3 Is there a system in place for independent review of study results?				7.7.2

Comments:

All source documents must be maintained to enable any independent data review.

Section 12: Limitations	Yes	No	N/A	Section Number
12.1 Does the protocol discuss the impact on the study results of:				
12.1.1 Selection bias?				7.8
12.1.2 Information bias?				7.8
12.1.3 Residual/unmeasured confounding? (e.g. anticipated direction and magnitude of such biases, validation sub-study, use of validation and external data, analytical methods).				7.8
12.2 Does the protocol discuss study feasibility? (e.g. study size, anticipated exposure uptake, duration of follow-up in a cohort study, patient recruitment, precision of the estimates)				7

Comments:

--

Section 13: Ethical/data protection issues	Yes	No	N/A	Section Number
13.1 Have requirements of Ethics Committee/ Institutional Review Board been described?				8
13.2 Has any outcome of an ethical review procedure been addressed?				
13.3 Have data protection requirements been described?				8

Comments:

There have been no ethical review procedures for this protocol to date.

Section 14: Amendments and deviations	Yes	No	N/A	Section Number
14.1 Does the protocol include a section to document amendments and deviations?				3

Comments:

--

Section 15: Plans for communication of study results	Yes	No	N/A	Section Number
15.1 Are plans described for communicating study results (e.g. to regulatory authorities)?				10
